## 4 INVESTIGATIONAL PLAN

### 4.1 Overall Study Design and Plan

This is a randomized, placebo-controlled, double-blinded, parallel group, multicenter study to evaluate the safety and efficacy of nemolizumab in patients suffering from PN. Approximately 70 adult patients suffering from PN for at least 6 months with severe pruritus defined by the mean of the worst daily intensity of the NRS score  $\geq 7$  over the previous week at baseline will be randomized in the study. Subjects meeting inclusion/exclusion criteria will be randomized in a 1:1 ratio to nemolizumab or placebo. Each subject will receive three subcutaneous injections of 0.5mg/kg of nemolizumab or matching placebo. Injections will be administered every 4 weeks (at baseline, week 4 & week 8).

Subjects' participation in the study will be up to 22 weeks, including an up to 4-week screening period, a 12-week treatment period (last study drug injection at week 8) and a 6-week follow-up period (10 weeks after the last study drug injection corresponding to 5 half-lives of nemolizumab).

Assessments of efficacy, safety, PK, PD, and biophysical will be conducted throughout this clinical trial. Refer to Appendix 1 for the complete schedule of assessments.

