  - $AUC_{0-t}$ : area under the concentration time curve calculated by the mixed linear logarithmic trapezoidal method from  $T_0$  up to the sampling time corresponding to the last quantifiable concentration ( $C_{last}$ )

From week 12 to week 18 (or Early termination or Unscheduled visit, if applicable):

- $t_{1/2}$ : the terminal half-life value ( $t_{1/2}$ ) will be calculated using the equation  $\ln 2/k$  after the last drug injection (week 8).
- $AUC_{0-t}$ : area under the concentration time curve calculated by the mixed linear logarithmic trapezoidal method from  $T_0$  up to the sampling time corresponding to the last quantifiable concentration ( $C_{last}$ ).
- $AUC_{0-\infty}$ : Area under the plasma concentration-time curve calculated by the mixed linear logarithmic trapezoidal method from  $T_0$  and extrapolated to time infinity as:  $AUC_{0-\infty} = AUC_{0-t} + C_{last} / k_{el}$ . When the extrapolation represents more than 20%,  $AUC_{0-\infty}$  and  $t_{1/2}$  will not be reported.

At weeks 4, 8, 12, 16, 18 (or Early termination or Unscheduled visit if applicable):

- $C_{trough}$ : The residual drug concentration
- Accumulation index: calculated with the serum nemolizumab trough concentration obtained 4 weeks after the first dose (week 4) and 4 weeks after last drug injection (week 18).

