### 5.9.2 Pharmacokinetic Parameters and Anti-drug Antibody Analyses

The PK parameters derived using non-compartmental techniques will be regarded as primary endpoints for the PK analyses (see Section 5.9.1). Primary inference for all the PK parameters will be based on the PKAP population.

The concentration at each time point will be summarized as arithmetic mean, standard deviation, median, minimum, and maximum, number of BLQs (Below the Limit of Quantification). Pharmacokinetic parameters using geometric means will be compared to determine when steady state conditions are achieved during the treatment period. Geometric means and between-subject coefficients of variation (CVb) will be calculated for loge-transformed AUC0-28d, Ctrough and Cmax where:

Geometric mean = exp(mean on log scale)

CVb (%) = sqrt[exp(SD) - 1] x 100

– where SD is the standard deviation of the loge-transformed data.

Following loge-transformation, Ctrough will be analyzed using analysis of variance (ANOVA), the model will include time and subject as a fixed effect. The residual variance from the model will be used to calculate point estimates and 90% CIs for the least squares means for each treatment formulation on the loge scale. These estimates will be back transformed to give point estimates and 90% CIs on the original scale.

The potential relationship between plasma concentrations of nemolizumab and change in pruritus NRS, biomarkers or other indicators of disease activity will be explored using PK/PD modeling, as appropriate.

Incidence of positive ADA results will be summarized by treatment group (absolute occurrence and percent of subjects). Individual PK profiles of subjects with or without ADA will be plotted to explore ADA impact on systemic exposure levels.

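### SAP 5.9.1 counts the Week 16 and 18 follow-up samples as Ctrough, so they enter the Ctrough ANOVA, and it bases the accumulation index on Week 18, which is not 4 weeks after the last injection.

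*SAP*

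**What the plan says.** **Dosing and follow-up.** SAP 4.1: "Injections will be administered every 4 weeks (at baseline, week 4 & week 8"). The same section describes "a 12-week treatment period (last study drug injection at week 8) and a 6-week follow-up" period, and puts the end of follow-up "10 weeks after the last study drug injection corresponding to 5 half-lives of nemolizumab".

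**Definition of Ctrough.** SAP 5.9.1 determines it "At weeks 4, 8, 12, 16, 18 (or Early termination or Unscheduled visit if applicable") and defines it only as "The residual drug concentration". Nothing in the definition ties it to the end of a dosing interval. Protocol 7.3.2 (the supplied version, V00) has the same list of weeks.

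**Model.** SAP 5.9.2, like protocol 9.2.5, log-transforms Ctrough and fits an ANOVA in which "the model will include time and subject as a fixed effect". The residual variance then gives the 90% CIs of the "least squares means for each treatment formulation". No weeks are named.

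**Steady state.** A separate sentence in the same section says: "Pharmacokinetic parameters using geometric means will be compared to determine when steady state conditions are achieved during the treatment period".

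**Accumulation index.** The bullet after Ctrough in SAP 5.9.1 uses the Week 4 trough and a second trough. It describes the second trough as taken 4 weeks after the last injection and labels it Week 18. The supplied protocol has no such index.

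**The concern.** A trough is the concentration at the end of a dosing interval. With injections at Weeks 0, 4 and 8, the intervals end at Weeks 4, 8 and 12. By Weeks 16 and 18 the drug has been washing out for 8 and 10 weeks.

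Two results are exposed. First, an additive model with time and subject assumes that log-concentration profiles are parallel across subjects. During washout they are not: fast and slow eliminators move apart as time since the last dose grows. The model has nowhere to put that divergence except the residual, and the pooled residual sets the CI width at every week, including the three true troughs. Second, an index meant to show accumulation would show loss if it is computed from Week 18.

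**Working it through.** **Inputs from the documents.** Injections at Weeks 0, 4 and 8 (SAP 4.1). Terminal half-life about 2 weeks (protocol 1.3). Model terms and use of the residual variance (SAP 5.9.2). Planned group size 35 (SAP 5.10).

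**Assumed, not in the documents.** Mono-exponential decline with equal doses; half-life range 1.5 to 3 weeks; between-subject CV of elimination rate 0 to 40%; within-subject SD on the log scale 0.15 to 0.35.

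**Step 1: timing.** The plan's own figure reproduces: 18 − 8 = 10 weeks, and 10 / 2 = 5 half-lives. Likewise 16 − 8 = 8 weeks and 12 − 8 = 4 weeks. The sample taken 4 weeks after the last injection is therefore Week 12. The accumulation-index bullet gives Week 18, and its two descriptions cannot both be true.

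**Step 2: expected profile.** By superposition, C(t) is proportional to the sum of exp(−k(t − d)) over doses d given before t, with k = ln 2 / 2 = 0.347 per week, so exp(−4k) = 0.25.

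| Week | Sum | Relative to Week 4 |
|---|---|---|
| 4 | 0.25 | 1.00 |
| 8 | 0.25 + 0.0625 = 0.3125 | 1.25 |
| 12 | 0.3125 + 0.0156 = 0.3281 | 1.31 |
| 16 | 0.3281 × 0.25 = 0.0820 | 0.33 |
| 18 | 0.3281 × 0.125 = 0.0410 | 0.16 |

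Weeks 16 and 18 are 25% and 12.5% of the Week 12 value.

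**Step 3: accumulation index**, taken as the later trough over the Week 4 trough. Week 12 / Week 4 = 1.31 (1.18 to 1.55 for half-lives of 1.5 to 3 weeks). Week 18 / Week 4 = 0.16 (0.07 to 0.39). The Week 18 version is below 1 throughout the range.

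**Step 4: why the late weeks reach the residual.** No dose falls between Weeks 12 and 18, so each subject's log concentration falls by exactly 6k. With a 20% CV, SD(k) = 0.20 × 0.347 = 0.069, and the fall varies between subjects with SD 6 × 0.069 = 0.42. Between true troughs the effect is small. The log ratio of Week 8 to Week 4 is ln(1 + exp(−4k)). Its slope in k is −4 × 0.25 / 1.25 = −0.8, which gives an SD of about 0.8 × 0.069 = 0.06.

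**Step 5: effect on CI width.** Two-way ANOVA on simulated log Ctrough, with subject and categorical time, 35 subjects, 2,000 runs and complete data. The entries are the square root of the ratio of mean residual variances, Weeks 4/8/12/16/18 over Weeks 4/8/12. This is the factor by which the 90% CI widens.

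| Within-subject log SD | CV 0% | 10% | 20% | 30% | 40% |
|---|---|---|---|---|---|
| 0.15 | 1.00 | 1.22 | 1.72 | 2.29 | 2.86 |
| 0.25 | 1.00 | 1.08 | 1.32 | 1.63 | 1.99 |
| 0.35 | 1.00 | 1.05 | 1.17 | 1.37 | 1.60 |

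If all subjects share one half-life, the late weeks cost nothing, because the time factor takes up the whole fall. The widening comes only from variation in elimination, and it shrinks as other within-subject noise grows.

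**The case against.** **The steady-state comparison is not contaminated.** A reader might infer that washout samples enter it and produce a false fall. Its own sentence confines it to the treatment period, which SAP 4.1 ends at Week 12. Nor does SAP 5.9.2 name the 90% CIs as the criterion for steady state; it says that geometric means will be compared. This part of the objection stands in full.

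**The ANOVA weeks are inferred.** SAP 5.9.2 lists none, and SAP 5.9.1 determines parameters only where appropriate. An analyst might leave out Weeks 16 and 18 unprompted. That is possible, but the only definition of Ctrough in the plan includes them and nothing excludes them. Following the text puts all five weeks in.

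**Inflation is not automatic.** This also stands. A factor of 1.7 or more needs both a CV of at least about 20% and a within-subject SD as low as 0.15, or higher CVs with more noise. The documents support no single value. The weekly estimates themselves are not shown to shift; only their stated precision changes.

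**Week 18 in the index may be a slip for Week 12.** Quite possibly, since the accompanying description fits Week 12. The two must still be reconciled, because a programmer working from the week label obtains 0.16.

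**The reference to formulations is surplus wording.** Agreed. There is one active product at one dose, and with subject as a fixed effect in a parallel-group trial a formulation term could not be separately estimated. The wording should be replaced; no term should be added.

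**Little depends on this.** Concentrations are also summarised at each time point, and no efficacy, safety or sample-size result uses Ctrough. That limits the weight of the point.

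**Conclusion.** The point holds for two things. First, Weeks 16 and 18 are labelled Ctrough although they are 8 and 10 weeks after the last injection, and the ANOVA does not keep them out. The 90% CIs at Weeks 4, 8 and 12 may be wider than they need be, by a factor anywhere from 1.0 to about 2.9 under the assumed CV of 0 to 40% and log SD of 0.15 to 0.35. Second, the accumulation-index bullet contradicts the dosing schedule. Computed from Week 18, the index would be about 0.16 where about 1.31 is expected, assuming a 2-week half-life and simple superposition. This second defect does not depend on the unknown variability.

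The documents do not support the further conclusions that the steady-state assessment is wrong or that the widening is certain. SAP 5.9.2 treats the PK parameters as primary for the PK analyses, but within the trial these are secondary results. The text should be corrected; nothing in the efficacy conclusions turns on it.

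**What to change.** - In SAP 5.9.1, define Ctrough as the concentration at the end of a 4-week dosing interval, at Weeks 4, 8 and 12. Report Weeks 16 and 18 as washout concentrations used for the terminal slope and half-life.
- In SAP 5.9.2, state that the Ctrough ANOVA uses Weeks 4, 8 and 12, that time is categorical, and that least squares means with 90% CIs are given by week. This replaces the wording about formulations.
- Define the accumulation index as the Week 12 trough (4 weeks after the last injection) over the Week 4 trough. Restricting the Ctrough weeks alone would leave this bullet asking for a Week 18 trough.
- Align the current protocol text corresponding to sections 7.3.2 and 9.2.5, or record the difference in SAP 5.11.

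The cost is wording in the SAP and the matching protocol sections. Sampling and data collection do not change.

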6.5 Study drug discontinuation

The study drug must be permanently discontinued when any of the following conditions is reported for a subject during the clinical trial:

- Serious immediate-type allergic manifestations including anaphylactic reaction
- Diagnosis of a malignancy (except curatively treated *in situ* cervical carcinoma or basal cell carcinoma)
- Pregnancy
- Any opportunistic infection (such as active TB and other infections whose nature or course suggest an immune-compromised status)
- Other systemic rescue therapies for PN (such as cyclosporine, thalidomide, gabapentin, phototherapy)
- Asthma/ worsening of asthma reported as a serious adverse event

In the event that the study drug is discontinued, the subjects should remain in the study and will be asked to return for all remaining visits and all assessments (including daily assessments of pruritus and sleep disturbance) according to [Table 2](#), except those who withdraw their consent for study participation or in case of pregnancy.

In the event of a missed dose (i.e. temporary discontinuation of the study drug), it will be documented in the eCRF that the drug has not been administered at the study visit, together with the reason (e.g. for safety reason). Subjects will be asked to return to the investigational sites for all remaining visits and complete all study assessments and procedures as described in Table 2.

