7.3.1 Technical procedures for pharmacokinetic blood sampling

At each sampling time for PK assessment, 2 mL of blood will be collected for the assessment of nemolizumab concentrations in serum samples.

For ADA assessment, 2 mL of blood will be collected at the same time as PK sampling.

PK samples are to be collected before drug injection (pre-dose samples) at Baseline, weeks 4, 8; the maximum allowed time windows for PK blood sampling is 30 minutes before drug injection. At weeks 1, 2, 12, 16 and 18 blood samples will be collected at the corresponding usual time of drug injection with an allowed time window of ± 1 h.

The date and time of collection for each sample along with the time of the last study drug injection and missed injections have to be recorded on the eCRF.

Processing of blood samples for PK and ADA assessments will be described in a specific manual.

Volumes of blood to be obtained for PK, ADA tests are summarized in [Appendix 1](#).

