#### **4.2.4 Pharmacokinetic and Anti-drug Antibody Assessments**

Blood samples will be collected to determine the PK profile of nemolizumab and to assess anti-drug antibodies (ADA). The serum concentration of nemolizumab will be assessed at baseline, weeks 1, 2, 4, 8, 12, 16, 18, and in case of early termination or unscheduled visit for safety reasons. ADA will be assessed at baseline, weeks 4, 8, 12, 16 and 18, and in case of early termination or unscheduled visit for safety reason.

Results will be described in the bioanalytical report, which will be included as an appendix in the final clinical study report.

Nemolizumab serum concentrations will be determined using validated ELISA method by a sponsor representative. A bioanalytical plan describing the details of the bioanalytical work related to serum samples of nemolizumab assessment will be written before the beginning of the sample analysis.

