### 5.9 Pharmacokinetic and Pharmacodynamics Evaluations

#### 5.9.1 Pharmacokinetic Parameter Calculation Methods

Derivation of PK parameters will be the responsibility of Quantitative Clinical Development (QCD), PAREXEL International. PK parameters will be calculated by non-compartmental analysis methods from the concentration-time data using Phoenix® WinNonlin® (WNL) Professional (Version 6.3 or higher). The following guidelines will be applied:

- Actual sampling times relative to dosing will be used in the calculation of all derived PK parameters. If the dosing time is not available for the calculation of actual sample time or the sample collection time is not available, the nominal time as recorded in the database will be used in the calculation. The listing of serum concentrations will note any instance in which a nominal time is presented in place of an actual sample time.
- BLQs at the beginning of a subject profile (i.e., before the first incidence of a measurable concentration) will be assigned to zero.
- BLQs at the end of a subject profile (i.e., after the last incidence of a measurable concentration) will be set to missing.
- Single BLQs which fall between two measurable concentrations will be set to missing.
- Consecutive BLQs which fall between measurable concentrations will be set to missing.
- Data from subjects with missing concentration values (missing samples) may be used if pharmacokinetic parameters can be estimated using the remaining data points.

Derivation of the pharmacokinetic parameters for nemolizumab will be performed using the following guidelines:

- $C_{max}$  will be obtained directly from the concentration-time data.
- $T_{max}$  is the time at which  $C_{max}$  is observed.
- $T_{last}$  is the time of the last quantifiable concentration.
- $\lambda_z$  will be estimated at terminal phase by linear regression after log-transformation of the concentrations:
  - Only those data points that are judged to describe the terminal log-linear decline will be used in the regression.
  - A minimum number of three data points in the terminal phase will be used in calculating  $\lambda_z$  with the line of regression starting at any post- $C_{max}$  data point ( $C_{max}$  should not be part of the regression slope). The adjusted correlation coefficient ( $R^2$  adjusted) in general should be greater than 0.80. Any value < 0.80 will be excluded from the analysis.

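### SAP 5.9.1 labels the second trough of the accumulation index week 18, but four weeks after the last injection (week 8) is week 12

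*SAP*

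**What the plan says.** SAP 5.9.1 lists the trough concentration at weeks 4, 8, 12, 16 and 18 and then an accumulation index built from two of these troughs. The index uses those obtained "4 weeks after the first dose (week 4) and 4 weeks after last drug injection (week 18"). No formula is given.

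The date of the last injection is stated elsewhere in the SAP:

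- In SAP 5.9.1 itself, the terminal half-life is to be calculated "after the last drug injection (week 8").
- SAP 4.1 gives injections at baseline, week 4 and week 8, and describes a "12-week treatment period (last study drug injection at week 8").
- SAP 4.1 places the end of follow-up, which is the week 18 visit, "10 weeks after the last study drug injection corresponding to 5 half-lives of nemolizumab".

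On sampling, SAP 4.2.4 states: "The serum concentration of nemolizumab will be assessed at baseline, weeks 1, 2, 4, 8, 12, 16, 18". Protocol 7.3.1 adds: "PK samples are to be collected before drug injection (pre-dose samples) at Baseline, weeks 4, 8". The week 4 sample therefore reflects the first dose only, and there is a scheduled sample at week 12, when no injection is given.

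**The concern.** The words and the week number in the definition select different samples. The words give two matching four-week intervals, one after the first dose and one after the last, which is what an accumulation index needs. The label replaces the second sample with one taken after a much longer drug-free interval.

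The label is what a programmer selecting records by visit would use. Week 18 exists in the data and appears in the list of trough visits, so nothing would flag the choice as an error. The result would be a ratio of a washout level to a four-week trough, reported under the name of accumulation. Some subjects might also drop out of it, because SAP 5.9.1 says: "BLQs at the end of a subject profile (i.e., after the last incidence of a measurable concentration) will be set to missing". A subject below the quantification limit at week 18 would then have no index. The documents give no quantification limit, so the number of such subjects cannot be estimated.

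**Working it through.** **Step 1. The calendar.** The inputs are the last injection at week 8 / Day 57 (SAP 5.9.1, SAP 4.1, protocol 8.1.2.3), week 12 / Day 85 (protocol 8.1.2.4) and week 18 / Day 126 (protocol 8.1.3.2).

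- Four weeks after the last injection: 8 + 4 = week 12, or Day 57 + 28 = Day 85. This is a scheduled PK sample.
- Week 18 in relation to the last injection: 18 - 8 = 10 nominal weeks, or 126 - 57 = 69 days (9.9 weeks).
- Visit windows are ±2 days at week 8 and ±7 days at week 18. The shortest possible interval is 69 - 2 - 7 = 60 days, still 32 days longer than 28.
- Week 18 would be four weeks after the last injection only if that injection were at week 14. Neither document has one.

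The SAP's week 18 label therefore cannot be reproduced from its own schedule. The answer is week 12.

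**Step 2. The size of the effect.** The documents give a terminal half-life of around 2 weeks (protocol 1.3). The assumptions are three equal doses at 0, 28 and 56 days, mono-exponential decline, additive contributions, and an index equal to the later trough divided by the week 4 trough. Write h for the half-life in days, and express each dose's contribution t days later as 2^(-t/h).

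- Week 4 (28 days, before the second injection): 2^(-28/h)
- Week 12 (84 days): 2^(-84/h) + 2^(-56/h) + 2^(-28/h)
- Ratio, week 12 / week 4 = 1 + 2^(-28/h) + 2^(-56/h)
- From Day 85 to Day 126 there are 41 dose-free days, so ratio, week 18 / week 4 = (week 12 ratio) × 2^(-41/h)

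With h = 14:

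- Week 12 / week 4 = 1 + 2^(-2) + 2^(-4) = 1 + 0.25 + 0.0625 = 1.3125
- Week 18 / week 4 = 1.3125 × 2^(-41/14) = 0.172. With a nominal 42 days the result is 1.3125 × 2^(-3) = 0.164.

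Sensitivity to the half-life (10 and 21 days are assumed bounds):

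| Half-life | Week 12 / week 4 | Week 18 / week 4 |
|---|---|---|
| 10 days | 1.16 | 0.07 |
| 14 days | 1.31 | 0.17 |
| 21 days | 1.55 | 0.40 |

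Across this range the week 12 ratio stays above 1 and the week 18 ratio well below 1. Step 1 needs none of these assumptions; only the sizes in step 2 do.

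**The case against.** The best defence is that the intent is plain. The words are parallel, the week 8 date is in the same section, and an analyst who follows the words makes no error. SAP 5.9.1 also bases derived parameters on actual sampling times relative to dosing, and a PK scientist would question an accumulation index near 0.2. The week 12 trough is reported in any case, and SAP 5.9.2 does not name the index among the parameters given geometric means. All of this stands, and it is why the point is minor. It does not make the label right. The label names the sample to be used for a stated parameter, and there is no formula to settle the conflict.

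A reader might infer three stronger things that the documents do not support.

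- **That missed injections are part of the error.** Protocol 6.5 provides for this case ("In the event of a missed dose (i.e. temporary discontinuation of the study drug")) and keeps such subjects attending visits. If week 12 were fixed for everyone, a subject who missed the week 8 injection would have an index of 2^(-2) + 2^(-4) = 0.31. But the SAP's words are tied to the last injection actually given. For that subject they select the week 8 sample, giving 1 + 2^(-2) = 1.25. If only the week 4 injection is missed, the words still select week 12, giving 1 + 2^(-4) = 1.06. An explicit rule would help, but limiting the index to fully dosed subjects is a design choice.
- **That this is the only definition of the index.** It is absent from the PK parameter list in section 7.3.2 of the protocol supplied (V00, 30 May 2017). The SAP is based on protocol Amendment 2.0 of 9 April 2018, which was not available to check.
- **That the AUC0-18W definition shows the same fault.** It refers to 24 weeks after dosing, but its own sample list ends at week 18. That is a separate editorial slip that resolves itself.

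**Conclusion.** The label is wrong on the SAP's own dates: the trough four weeks after the last injection is week 12. If the label were followed, the index would be about 0.17 instead of about 1.31 and could not be read as accumulation. Those sizes rest on a half-life of about 2 weeks, equal doses, log-linear decline and a later-to-first ratio; the calendar error does not depend on them.

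Severity is minor. One descriptive PK parameter is affected, no data are lost, no stated decision uses the index, and the primary efficacy analysis is untouched. It would be wrong to infer that the trough summaries or the PK characterization as a whole are compromised.

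**What to change.** In SAP 5.9.1, change the week number attached to the second trough from 18 to 12 and add the formula: accumulation index = Week 12 trough / Week 4 trough, for subjects dosed at baseline, week 4 and week 8.

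Optional clarification: state how subjects with a missed injection are handled and report the number of subjects contributing.

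Separate editorial change: in the AUC0-18W definition, replace 24 weeks with 18 weeks.

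The cost is one label and one formula line, plus one number for the editorial item. The week 4 and week 12 samples are already scheduled, so no new data are needed.
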